8.2 Reporting of Serious Adverse Events and Unanticipated Problems

When an adverse event has been identified, the study team will take appropriate action necessary to protect the study participant and then complete the Study Adverse Event Worksheet and log. The sponsor-investigator will evaluate the event and determine the necessary follow-up and reporting required.

8.2.1 Sponsor-Investigator reporting: notifying the Mayo IRB

Information collected on the adverse event worksheet (*and entered in the research database*):

- Subject's name:
- Medical record number:
- Disease/histology (if applicable):
- The date the adverse event occurred:
- Description of the adverse event:
- Relationship of the adverse event to the research (drug, procedure, or intervention*):
- If the adverse event was expected:
- The severity of the adverse event: (use a table to define severity scale 1-5**)
- If any intervention was necessary:
- Resolution: (was the incident resolved spontaneously or after discontinuing treatment)
- Date of Resolution:

The Investigator will review all adverse event reports to determine if specific reports need to be made to the IRB and FDA. The sponsor-investigator will report to the Mayo IRB any UPIRTSOs and NonUPIRTSOs according to the Mayo IRB Policy and Procedures. The sponsor-investigator will sign and date the adverse event report when it is reviewed. For this protocol, only directly related SAEs/UPIRTSOs will be reported to the IRB.

Relationship

The relationship of an AE to the Investigational Drug is a clinical decision by the sponsor-investigator (PI) based on all available information at the time of the completion of the CRF and is graded as follows:

1. Not related: a reaction for which sufficient information exists to indicate that the etiology is unrelated to the study drug; the subject did not receive the study medication or the temporal sequence of the AE onset relative to administration of the study medication is not reasonable or the event is clearly related to other factors such as the subject's clinical state, therapeutic intervention or concomitant therapy.
2. Unlikely: a clinical event, including laboratory test abnormality, with a temporal relationship to drug administration which makes a causal relationship improbable and in which other drugs, chemicals, or underlying disease provide plausible explanations.
3. Possible: a clinical event, including laboratory test abnormality, with a reasonable time sequence to administration of the drug but which could also be explained by concurrent disease or other drugs or chemicals; information on drug withdrawals may be lacking are unclear.
4. Probable: a clinical event including laboratory test abnormality, with a reasonable time sequence to administration of the drug, unlikely to be attributed to concurrent disease or other drugs or chemicals and which follows a clinically reasonable response on withdrawal (de-challenge): re-challenge information is not required to fulfil this definition.
5. Definite: a reaction that follows a reasonable temporal sequence from administration of the drug, or in which the drug level has been established in body fluids or tissues, that follows a known or expected response pattern to the suspected drug, and that is confirmed by improvement on stopping or reducing the dosage of the drug, and reappearance of the reaction on repeated exposure (re-challenge).

Severity

The maximum intensity of an AE during a day should be graded according to the definitions below and recorded in details as indicated on the CRF. If the intensity of an AE changes over a number of days, then separate entries should be made having distinct onset dates.

1. Mild: AEs are usually transient, requiring no special treatment, and do not interfere with patient's daily activities.
2. Moderate: AEs typically introduce a low level of inconvenience or concern to the patient and may interfere with daily activities, but are usually ameliorated by simple therapeutic measures.
3. Severe: AEs interrupt a patient's usual daily activity and traditionally require systemic drug therapy or other treatment.

8.2.2 Sponsor-Investigator reporting: Notifying the FDA

The sponsor-investigator will report to the FDA all unexpected, serious suspected adverse reactions according to the required IND Safety Reporting timelines, formats and requirements.

Unexpected fatal or life threatening suspected adverse reactions where there is evidence to suggest a causal relationship between the study drug/placebo and the adverse event, will be reported as a serious suspected adverse reaction. This will be reported to the FDA on FDA Medwatch Form 3500A, no later than 7 calendar days after the sponsor-investigator's initial receipt of the information about the event.

Other unexpected serious suspected adverse reactions where there is evidence to suggest a causal relationship between the study drug/placebo and the adverse event, will be reported as a serious suspected adverse reaction. This will be reported to the FDA on FDA Medwatch Form 3500A, no later than 15 calendar days after the sponsor-investigator's initial receipt of the information about the event.

Any clinically important increase in the rate of serious suspected adverse reactions over those listed in the protocol or product insert will be reported as a serious suspected adverse reaction. This will be reported to the FDA on FDA Medwatch Form 3500A no later than 15 calendar days after the sponsor-investigator's initial receipt of the information about the event.

The sponsor-investigator must also notify the FDA (and sponsors must notify all participating investigators) in an IND safety report of potential serious risks, from clinical trials or any other source, as soon as possible, but in no case later than 15 calendar days after the sponsor determines that the information qualifies for reporting under § 312.32(c)(1)(i)-(iv).

Findings from other studies in human or animals that suggest a significant risk in humans exposed to the drug will be reported. This will be reported to the FDA on FDA Form 3500A, no later than 15 calendar days after the sponsor-investigators initial receipt of the information about the event.

8.3 Unmasking/Unblinding Procedures

The investigational drug blind shall not be broken by the investigator unless information concerning the investigational drug is necessary for the medical treatment of the subject. In the event of a medical emergency, if possible, the sponsor-investigator or PI should be contacted before the investigational drug blind is broken to discuss the need for unblinding.

If the PI decides emergency unblinding is medically necessary, the PI needs to contact the Research Pharmacy. The sponsor-investigator must be notified as soon as possible if the investigational drug blind is broken. The date, time, and reason the blind is broken must be recorded in the source documents, CRFs or Event forms/logs.

8.4 Stopping Rules

A pre-specified safety assessment will be conducted after 20 subjects (5 per arm) have completed a one-week safety follow up period. Initial reports will maintain blinding of study arms. If any study arm reports a serious adverse event or ≥ 2 total adverse events that are possible, probable, or definite relation to the investigational study drug, study arms will be unblinded and data provided to an independent monitor as specified in the DSMB. Active high dose arms may be stopped early if safety concerns arise related to the investigational drug.

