Eligible subjects will be seen at the clinical trial research unit (CTR) to receive the influenza vaccination (Fluzone, high-dose split virion influenza virus vaccine, Sanofi Pasteur) and a single IM injection of the study drug (entolimod or placebo). For safety assessment, initially 8 patients were to be enrolled in arm 1 (1ug) and accrual temporarily halted until the DSMB had assessed early adverse events. Due to the late seasonal start only four patients were successfully accrued to the study by the end of the flu season. A safety report was generated and the DSMB endorsed proceeding with enrollment of arm 2 (3ug) and arm 1 will restart. After 8 subjects have been enrolled into arm 2, accrual for arm 2 will be temporarily halted until the DSMB has assessed early adverse events. A safety report will be generated and enrollment of arm 3 (10ug) will commence and arm 2 will restart. After 8 subjects have been enrolled into arm 3, accrual for arm 3 will be temporarily halted until the DSMB has assessed early adverse events. A safety report will be generated and enrollment of all three arms will continue until enrollment is complete.

Unblinded and subject-level adverse event data will be provided to the Data Safety Monitoring Board (DSMB). If there is any evidence that higher doses are associated with adverse events, those study arms may be dropped, and the remaining planned patients accrued and randomized to remaining dose levels (and placebo) in equal proportions.

Subjects will be evaluated at the CRTU on the day of study drug administration (Day 1), for ≥ 6 hours (2hrs, 4hrs and 6 hrs), thereafter day 2, weeks 1 and 4, and then on months 2, 6 and 12. Between month 2 and 6 and 6 and 12 AEs will be reported and occurrence of respiratory infections will be assessed via phone interviews. Assessments of adverse events (AEs), vital signs/oxygen saturation including orthostatic measurements, clinical chemistry and hematology parameters (i.e., complete blood count with differential), ECGs, plasma cytokines, leukocytes, anti- A/H1N1, anti-A/H3N2, and anti-B influenza serum circulating antibodies including cellular immune response outcomes will be performed to describe drug safety, pharmacodynamics, and immunogenicity.

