5.3 Method for Assigning Subjects to Treatment Groups

Study subjects will be randomized in a dose-escalated 4-arm study of entolimod in 3 possible doses or placebo (see table 2 below). Beginning in period 1, the first eight patients in the 1ug arm will be evaluated for safety and tolerability by the DSMB prior to the enrollment of the remainder of the 1ug arm. In addition, after review we will proceed with recruitment in period 2 of the 3ug arm. Again, safety and tolerability will be assessed in the first 8 patients of the 3ug arm during period 2. Similarly, after evaluation by the DSMB we will proceed with the remainder of the 3ug arm. In period 3 we will evaluate safety and tolerability in the first 8 subjects of the 10ug arm. An evaluation by the DSMB will be completed and we will proceed with the remainder of the 10ug arm until all subjects have been accrued. We will recruit the balance of the subjects remaining to be enrolled (to obtain 25 subjects per arm) pending safety review by the DSMB.

Randomization will be performed using Medidata Balance software, integrated into the electronic case report forms Medidata RAVE. A permuted block design will be used, with stratification by sex. Subjects and study center personnel involved in the care of subjects will be blinded to study drug assignment (entolimod vs. placebo).

Table 2. Dose-Escalated 4-arm Study

Arm	Placebo	1ug	3ug	10ug
Period 1	2	6		
Period 2	2		6	
Period 3	2			6

Dose Levels

Cohorts of subjects will be sequentially enrolled at progressively higher starting dose levels. The following dose levels are planned:

- Dose Level 1: 1 μ g
- Dose Level 2: 3 μ g
- Dose Level 3: 10 μ g

These doses are within the dose range of 1 μ g to 10 μ g and equal or greater than five times less than that which has been previously evaluated in healthy subjects and patients with advanced solid tumors.

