7.3 Subject Population(s) for Analysis

The primary analysis uses a modified intent-to-treat principle. Patients will be analyzed based on randomized arm using methods described previously. Exploratory analyses will assess whether a differential sex-based response to treatment exists for the primary outcomes and secondary outcomes of FI and QOL, using interaction terms in regression models.

8 Safety and Adverse Events

For safety analyses, AEs will be classified using the Medical Dictionary for Regulatory Activities (MedDRA). The severity of AEs will be graded by the investigator according to the Guidance for Industry Toxicity Grading Scale for Healthy Adult and Adolescent Volunteers Enrolled in Preventive Vaccine Clinical Trials. Concomitant medication use will be coded using the World Health Organization Drug Dictionary (WHODRUG) into Anatomical Therapeutic-Chemical classification (ATC) codes; these data descriptions will particularly focus on supportive medications and care provided in response to any study-study-induced adverse effects and to therapies for GVHD. For ECG assessment of QT intervals, correction by both the Bazett and Fridericia methods will be applied, and the data will be summarized by CTCAE grading categories in terms of absolute QTc and maximal QTc change from baseline.

A safety analysis will be conducted after 20 patients (5 per arm) have been randomized and completed the one-week safety follow-up period. After the last subject has completed their one-week safety follow-up period, there will be a temporary halt in additional participation pending analysis of safety outcomes, anticipated to be no longer than seven days. A safety report will be generated after the 20th patient completes 1 week follow up, summarizing all adverse events overall and by study arm while maintaining blind (groups denoted as A-D in random order). If appropriate, as described below, unblinded and subject-level adverse event data will be provided. Adverse events, both short term (14 days) and long term (through 365 days), will continue to be collected with ongoing monitoring as specified in the Data Safety Monitoring Plan (DSMP).

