10.1 Study Monitoring Plan

This study will utilize a Data and Safety Monitoring Board (DSMB) to provide a system for appropriate oversight and attention to the protection of human subjects and quality assurance. The DSMB will have the following monitoring activities: (1) Review of a pre-specified safety assessment after 6 subjects in each arm have completed safety follow-up period day 1; If the DSMB determines that it is safe to proceed the next dose will be administered and a safety assessment will be performed to determine if it is safe to continue to the highest dosing of 10ug; (2) prospective review of any issues related to the safety of subjects; and (3) regular review (i.e., twice yearly) of measures designed to protect the validity of the data and the integrity of the research study. With regard to monitoring activity (2), safety issues will include the timely review of all SAEs (within 24 hours) and the regular review (every 3 months) of all AEs. With regard to monitoring activity 3, the DSMB will review with the principle investigator and lead study coordinator the methods in which data is collected, stored, and protected, including review of randomly selected subject case report and other forms. The DSMB will also identify when to terminate a subject's participation by following prescribed individual stopping rules and when to terminate the study by following prescribed study stopping rules. Prescribed individual stopping rules will include the following: (1) Any SAE that precludes further participation of the subject; (2) With respect to subjects that have not received study drug, any SAE related to the study drug that in the opinion of the principle investigator or DSMB places subjects at high risk of

experiencing the same SAE; (3) if in the opinion of the principle investigator, there is doubt that a subject, for any reason, can continue to fully participate in the study. Prescribed study stopping rules will include the following: (1) dose-limiting toxicities as defined elsewhere in this document in ≥ 2 subjects for the lowest dose concentration of study drug. See also section 8.4, *Stopping Rules*. This will not preclude the analysis of pre-existing data.

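### The adverse-event trigger and enrolment halt are tied to a 20-subject, five-per-arm look that does not fit the dose-escalation cohorts and falls after both dose steps

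*Combined protocol and SAP*

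**What the plan says.** Section 8.4 sets the look: "A pre-specified safety assessment will be conducted after 20 subjects (5 per arm) have completed a one-week safety follow up period". If any arm then shows a serious adverse event, or two or more events rated possibly, probably or definitely related, the arms are unblinded and the data go to an independent monitor. The opening text of section 8 repeats the look ("A safety analysis will be conducted after 20 patients (5 per arm) have been randomized and completed the one-week safety follow-up period") and adds that "there will be a temporary halt in additional participation pending analysis of safety outcomes, anticipated to be no longer than seven days".

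Escalation itself runs through cohorts. Table 2 in section 5.3 gives each period six subjects on the new dose and two on placebo. Section 3 makes the steps sequential; after the 3 µg review, "A safety report will be generated and enrollment of arm 3 (10ug) will commence and arm 2 will restart". It also records that "Due to the late seasonal start only four patients were successfully accrued to the study by the end of the flu season". The DSMB then endorsed opening 3 µg, and the 1 µg arm restarts.

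For the timing of the cohort reviews, section 5.3 says "Again, safety and tolerability will be assessed in the first 8 patients of the 3ug arm during period 2", with no length of follow-up. Section 3 refers only to early events. Section 10.1 says "Review of a pre-specified safety assessment after 6 subjects in each arm have completed safety follow-up period day 1".

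**The concern.** The trigger and the halt assume four arms filling in parallel, while the design fills them one dose at a time. If the five-per-arm state arises only after 10 µg has opened, the one numerical rule for related non-serious events at the higher doses is not applied when the DSMB decides whether to escalate.

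Safety is a primary objective, the subjects are 65 or older, and the step from 3 to 10 µg is still ahead. Staff also need to know which follow-up to wait for before each review, and the sections do not give one answer.

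**Working it through.** **Inputs.** Look: 20 subjects, five in each of four arms, one week (sections 8 and 8.4). Cohorts: 6 active + 2 placebo per period (Table 2). Period 1 accrual: 4 subjects, split not given (section 3). 10 µg opens after the 3 µg review (section 3).

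**1. The plan's figure.** 5 × 4 = 20 is correct arithmetic. The cohorts do not lead there: Table 2 accumulates to 8, 16 and 24.

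**2. Composition at 20 with full Table 2 cohorts.** After 16 subjects there are 4 on placebo, 6 on 1 µg, 6 on 3 µg and none on 10 µg. The next four come from period 3 and include 0 to 2 placebo. The arms (placebo/1/3/10 µg) are then 4/6/6/4, 5/6/6/3 or 6/6/6/2. The 10 µg arm never has five.

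**3. Smallest total with at least five in every arm.** Sum, over arms, the larger of 5 and the number already required before 10 µg opens.

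| Reading | Sum | Total |
|---|---|---|
| Period 1 stopped at 4, then 6 on 3 µg | 6+5+5+5 | 21 |
| Full Table 2 cohorts | 6+6+5+5 | 22 |
| Period 1 stopped at 4, 8 on 3 µg | 8+5+5+5 | 23 |
| 8 on 1 µg and 8 on 3 µg | 8+8+5+5 | 26 |

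All of these exceed 20, and all include five subjects already on 10 µg.

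**4. The 10 µg count at the 20th subject on the path in section 3.** Let r be the number of restarted arm 1 subjects (1 µg or placebo) who enter before 10 µg opens. The documents do not give r, so a range is shown. 10 µg opens at 4 + 8 + r = 12 + r subjects, leaving 8 − r of the first 20 to come from period 3, of whom at most two are on placebo.

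| r | Subjects on 10 µg at n = 20 |
|---|---|
| 0 | 6 |
| 1 | 5–6 |
| 2 | 4–6 |
| 4 | 2–4 |
| 6 | 0–2 |
| 8 or more | 0 |

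With r = 0 the 10 µg cohort is complete, but at most four subjects are on 1 µg, so five per arm still fails. Restarts that enter after 10 µg opens can only lower the 10 µg count.

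**5. Follow-up at the reviews that gate a dose.**

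| Place | Follow-up before review |
|---|---|
| Section 3 | early events, no length |
| Section 5.3 | no length |
| Section 10.1 | day 1 |

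One week appears only for the 20-subject look, which gates nothing.

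**6. Other numerical rules.** Section 10.1 has a study stopping rule of dose-limiting toxicity in two or more subjects, but only at the lowest dose, and section 1.6.1 leaves that toxicity to the investigator's judgement. No other count covers related non-serious events at 3 or 10 µg.

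**The case against.** The strongest answer is that little safety control is lost. Section 8.5.1 gives an unblinded DSMB all adverse event reports, has it meet every other week during enrolment, and lets it decide each dose step. Section 10.1 has serious events reviewed within 24 hours. Section 3 sets a low bar for action: "If there is any evidence that higher doses are associated with adverse events, those study arms may be dropped". The trigger only unblinds and refers data. All of this stands. A reader might infer that escalation proceeds without safety monitoring; the documents show the opposite.

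Three other strong readings also fail.

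- That five per arm at 20 can never occur. It can if a cohort departs from 6+2. Randomisation is in permuted blocks stratified by sex, and block size is not given. Assuming 3:1 blocks of four, a cohort of five men and three women could be 5+3. Period 1 at 3+1, period 2 at 5+3, two restarts on 1 µg and 5+1 in period 3 then give 5/5/5/5. It can also occur if the rule counts completers and one of six 3 µg subjects misses Day 7. In either case five subjects have already had 10 µg.
- That the halt has no date. Section 8 times the report from the 20th patient's one-week follow-up, which can be counted. What is undefined is the composition at that date.
- That the gating reviews carry three conflicting follow-up times. They carry day 1 or none, and the unspecified wording is compatible with day 1.

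Two further points stand. Section 8.4 also says high-dose arms may be stopped early, and with six of 25 treated at 10 µg there are 19 still to come, so a later all-arm look has some use. And Day 7 is not plainly better than day 1. It is remote, whereas Day 1 has vital signs, laboratory tests and an ECG (sections 6.3 and 6.4), and the half-life is about 3 hours (section 1.4.2.1).

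**Conclusion.** The point holds as a rule that does not fit the design, with a gap in stated follow-up. With six on 3 µg before 10 µg opens, five in every arm needs at least 21 subjects, and 21 to 26 across the readings above. The 20th subject may arrive with 0 to 6 on 10 µg. Whichever reading is taken, a look with five per arm follows both dose steps, so the plan's own count for related non-serious events and its one-week follow-up do not inform either.

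This is a minor to moderate repair, because the DSMB's unblinded review, the 24-hour review of serious events and the freedom to drop arms remain in place. The floors rest on cohorts of 6+2 as printed in Table 2, or on eight active subjects under the alternative reading. The range 0 to 6 also rests on four subjects in period 1 and an unknown number of restarts.

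**What to change.** 1. In section 8.4, apply the existing trigger at each remaining cohort review. Suggested text: *At the 3 µg and then the 10 µg cohort review, once the cohort has completed the Day 7 contact, the DSMB reviews its adverse events unblinded. If any arm has a serious adverse event, or two or more events of possible, probable or definite relation to study drug, the DSMB records its decision and reason before the next dose level or the rest of that arm opens.* The 1 µg review, done at four subjects, is left as it is.
2. Print one follow-up time for these reviews in sections 3, 5.3, 8.4 and 10.1: Day 7, to match the one week in sections 8 and 8.4, or day 1 if the DSMB prefers.
3. Either delete the 20-subject look from sections 8 and 8.4, or restate it as an all-arm look when the 10 µg cohort completes one week. Drop the 20 and the five per arm in both cases.

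The trigger should prompt a recorded decision and not an automatic stop, because flu-like symptoms are expected (section 1.6.1). Counting subjects with an event, not events, is an option for the sponsor and not part of this correction.

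The cost is protocol wording. No subjects, visits or data are added, since Day 7 event review is already scheduled (section 6.4). If Day 7 is chosen, each of the two reviews waits up to about 7 − 1 = 6 days longer than a day 1 review, and it gains reported events only.
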